## 5.4. Adequacy of Protection Against Risks:

5.4.a. Recruitment and Informed Consent: Subjects will include male and female community college students (N=40 for Phase I and N=250 for Phase II) ages 18-29 who are current alcohol users and who report at least two heavy drinking (HD) episodes in the past two weeks (in one sitting: 5 or more drinks for men, 4 or more for women), who have a smartphone and use TxM. We will advertise for study participants using campus media outlets, in-class presentations, flyers, email and Internet sources we have used successfully in previous studies. 16,17,61 Before being posted, all flyers and advertisements will be reviewed by The Miriam Hospital Institutional Review Board (will serve as the IRB of record for the overall study) to ensure that descriptions of the study are clear and not misleading. All advertisements and presentations will include both the study phone number and website URL.

Interested persons responding to these ads will access the study's initial description on our website or speak with our research staff who are trained in the conduct of research and protections of human subjects' confidentiality and privacy. The study staff will explain the nature and purpose of the study, answer any questions, and will send the caller the link to our website if they are interested in enrolling. Individuals accessing the website will view a brief description of the study requirements, and be asked to click through to the study screener, if interested. If eligible, they will read and sign the online consent form using an electronic signature by clicking a button indicating consent. Electronic consent for the screening questions is obtained prior to initiating the screener survey and prior to collecting baseline data. As part of the consenting process individuals will answer a series of true/false questions to ensure they understand the fundamentals of enrolling in a research study (e.g., this is a research study, your information is confidential, you may withdraw at any time, etc.). A phone number is also provided on the website so that individuals can call our study staff with any questions regarding the study or the consent.

All screening data will be collected anonymously until eligibility is determined and informed consent is signed. Eligible individuals who are interested in participating and who have provided signed consent will be asked to provide identifiers (e.g., name), contact information (e.g., phone number, email), and locator contact number (1-2 additional individuals who can be contacted if we are unable to reach the participant). Participants will be emailed a copy of the consent document. Data collected at screening for individuals who are determined to be ineligible will be retained as anonymous data (no identifiers). This will be explained to participants at the start of the screening process.

**5.4.b. Risk Minimization:** All study staff will be trained and certified in handling human subject information to maintain privacy and confidentiality. No survey data will be labeled with the participant's name or other identifying information, but will instead be linked to a study ID number. Documents linking study ID numbers to identifying information (e.g., name, address) will be stored electronically in an encrypted password-protected file. All paper-data (hard copies) with identifying information will be stored in locked file drawers, separate from any coded data. Documents with identifying information and documents linking study ID numbers to identifying information will be destroyed at the end of the study. All electronic data including data entered on through websites will be secured and encrypted. Subject information will be accessible only to research staff, who are pledged to confidentiality. Identifying information will not be reported.

Any emotional distress will be minimized by assurances that participants can refuse to answer any particular question they do not feel comfortable addressing and can withdraw from the study at any time without penalty. If any significant mental health problems are reported appropriate referrals will be arranged.

Any participants who are screened ineligible due to a high alcohol dependence score will be referred to local community health centers.

The Advisory Board will provide advice regarding implementation of the trial, including reviewing the recruitment materials, website and surveys to ensure acceptability to the student audience. Although the Advisory Board will help with recruitment, participant (student) data will not be shared with them. This will be clarified during recruitment/advertising so that students are not hesitant to join the study. Moreover, a Certificate of Confidentiality will be obtained from the Office of Human Research Protections (OHRP) to ensure the security and privacy of participants.

- **5.5. Potential Benefits of the Proposed Research to the Subjects and Others:** Participating in this study may heighten participant's motivation to stop or reduce drinking, and participants may benefit by having the opportunity to consider how alcohol is affecting their lives. Moreover, for those receiving the CARES or CYD programs, intervention content is designed to encourage reduced and responsible drinking and constitutes an active intervention that may result in reduced drinking among participants.
- 5.6. Importance of Knowledge to be Gained: The anticipated gains obtained through this study are substantial. Excessive alcohol use is the third-leading preventable cause of death in the U.S.¹ Young adults show the highest rates of hazardous alcohol use.²-⁵ In the U.S. community colleges serve over 12 million students,⁶ comprising 45% of all college students nationwide.⁶-ී Community college students (CCS) show rates of heavy alcohol use similar to students at traditional four-year residential colleges,³,9-1² but CCS are at higher risk for negative consequences of heavy drinking, including physical and sexual assault, fatal injuries, and driving under the influence. Despite the large number of CCS and their level of risk, *alcohol interventions for young adults have focused almost exclusively on students at traditional four-year residential colleges*.

The information derived from this study will be used to produce an effective, low-cost, easily disseminated intervention to help community colleges address student drinking - which could have significant impact on public health. Given how common and problematic student drinking problems are, we believe that the minimal risks described above are reasonable.

Younger adults tend to under-utilize alcohol treatment services delivered through traditional methods (e.g., in-person clinics, telephone hotlines). Dissemination of an evidence-based program designed this population that can be delivered as a smartphone app has the potential to reach a nationwide audience of young adults who might not otherwise receive intervention.

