## 4.3.b. Inclusion/Exclusion Criteria:

(1) age 18-29; (2) current CCS; (3) report ≥ two heavy (episodic) drinking (HEDs) in the past two weeks (This pattern is called Frequent Binge Drinking and should net a group of regular heavy drinkers); (an HED is defined as 5 [4] or more drinks in one sitting for men [women]); (4) has a smartphone and uses apps and text messaging; and (5) speaks and reads English comfortably.

Due to safety concerns, we will exclude participants who (1) receive a score >14 on the Alcohol Dependence Scale (indicating psychological to physical dependence), 116,117 or (2) report prior or current alcohol treatment (these individuals will be provided information about local treatment options).

- 4.3.c. Recruitment Procedures: Participants will be recruited through flyers, classroom presentations, and emails to students at CCRI and BCC. Ads will provide a brief description of the study, a study website and a contact phone number, allowing individuals to access information about the study by phone or internet. These recruitment and enrollment procedures have been used successfully in our previous studies. 16,18 Recruitment materials will emphasize that professors and community college administrators will not have access to information about participants. The website will provide a description of the study and an option to continue to online screening questions. For those calling by phone, study staff will briefly explain the study, answer questions, and direct interested callers to the website to complete screening. At the end of the screening survey, respondents will be asked to provide their community college email address. Our web-based survey system will be programmed to determine the eligibility of respondents, check the provided email address against prior respondents, and send the eligibility information only to valid email addresses (e.g., ccri.edu or bcc.edu) that have not previously been used. These procedures ensure that respondents will not be able to complete the screener more than once. Email addresses will be stored in a separate data table from screening responses (linked by a unique ID), allowing us to maintain confidentiality.

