Consented participants will proceed to the baseline survey. After completing the baseline survey, the online system will randomly assign them to an intervention condition using stratification by age (under/over 21), gender, and Audit-C scores (scores of >4 for men or >3 for women are considered hazardous drinking). Participants will immediately be informed of their condition and will be provided relevant information by email. This email also will contain summary information about the study, the consent form, the schedule of upcoming assessments, and compensation information. All randomized participants will be followed regardless of intervention completion. Our participant tracking system will allow us to track completion of all components, including consent, the baseline survey, and the assigned intervention. Eligible participants who do not complete enrollment or who enroll but do not complete the baseline survey will be contacted by phone.

4.4.c. Conditions:

**CARES:** Participants randomized to CARES will be texted or emailed a link to their appropriate App Store to download the *Live Inspired* app. *Live Inspired* will send a message containing a code that the participant must enter into the *Live Inspired app* (similar to verification codes used by online vendors) to gain access to the CARES program. Participants will set up an online profile and receive CARES app coaching messages for 12 weeks. The messages developed in our pilot study (section 4.2.) focus on alcohol education, caring messages, and strategies for risk reduction and are designed to increase self-efficacy and motivation to control/reduce

Message Type CCS Relevant Issue		Example message					
Safety messages targeting self-efficacy	CCS identified the need for messages on drinking safely: "Don'ttell me not to drink. Tell me you care how! drink"	When out partying, always be aware of your surroundings - and have an exit plan.					
Finding counseling in the community	Community colleges frequently do not have on-campus counseling or health services	Everyone needs help sometimes. If drinking is giving you problems, local counselors can help [phone #].					
Messages targeting work/school balance (Goal- setting themed)	CCS likely to have full or multiple part-time jobs.	You work hard and study hard. Set goals for yourself that are Personal, Possible, and Specific. And don't let drinking compromise all that hard work.					

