Approximately 56% of the students at BCC and CCRI are women. The current ethnic and racial distribution of the student population at CCRI and BCC are similar. Approximately 12% are Black/African American, 3% Asian, 1% Native American, 1% Native Hawaiian or Other Pacific Islander, 75% White and 8% more than one race. Approximately 20% of students are Hispanic. However, nationally enrollment at community colleges and similar 2-year institutions is approximately 50% ethnic and/or racial minority. Therefore we will over-recruit to ensure that approximately 50% of our study participants will be ethnic and/or racial minorities. This is similar to the overall population in the greater Providence, RI area. Both colleges maintain a small student services office, but health services are not available on campus.

5.1.c. Recruitment Procedures: Participants will be recruited through flyers, classroom presentations and emails to students meeting age criteria at CCRI and BCC. Ads will provide a brief description of the study, a study website and a contact phone number, allowing individuals to access information about the study by phone or internet. Recruitment materials will emphasize that community college professors and administrators will not have access to information about participants. The website will provide a description of the study and an option to continue to online screening questions. For those calling by phone, project research staff will briefly explain the study and answer any questions, then will direct interested callers to the website to complete the screening. At the end of the screening survey, respondents will be asked to provide their community college email address. Our web-based survey system will be programmed to determine the eligibility of respondents, check the provided email address against prior respondents, and send the eligibility information only to valid email addresses (e.g., ccri.edu or bcc.edu) that have not previously been used. These procedures will ensure that respondents will not be able to complete the screener more than once. Email addresses will be stored in a separate data table from screening responses (linked by a unique ID), allowing us to maintain confidentiality.

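### Section 5.4.a promises anonymous screening data, but the screener takes a college email tied to the answers and no step cuts that tie for ineligible people

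*Combined protocol and SAP*

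**What the plan says.** Section 5.4.a (Recruitment and Informed Consent) makes two statements about screening data. On collection: "All screening data will be collected anonymously until eligibility is determined and informed consent is signed". On retention: "Data collected at screening for individuals who are determined to be ineligible will be retained as anonymous data (no identifiers"). It then adds: "This will be explained to participants at the start of the screening process". The same paragraph places email among the contact details requested from people who have already signed consent.

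Section 5.1.c (Recruitment Procedures) describes how the screener works: "At the end of the screening survey, respondents will be asked to provide their community college email address". The system then decides eligibility, and it is also programmed to "check the provided email address against prior respondents". On storage: "Email addresses will be stored in a separate data table from screening responses (linked by a unique ID), allowing us to maintain confidentiality". Section 4.3.c gives the same procedure for Phase I, including that "respondents will be asked to provide their community college email address".

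Section 5.4.b has the only disposal rule that could apply: files that contain identities, or that connect study IDs to identities, are destroyed when the study ends.

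**The concern.** Two parts of one protocol describe the same data differently. Section 5.4.a treats screening answers as anonymous. Sections 4.3.c and 5.1.c attach a personal identifier to them before eligibility is known and before trial consent is given. Holding the two tables apart and joining them by an ID protects confidentiality, which is the word the protocol itself uses there. It is not anonymity, because whoever holds both tables can put a person to a set of answers.

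This matters for two reasons. First, section 5.3 names loss of confidentiality as the main risk in every phase. The answers in question (sections 4.3.f and 4.4.e) cover recent heavy drinking, the Alcohol Dependence Scale and past treatment for an alcohol problem. Second, section 5.4.a says consent to the screening questions is obtained before the screener starts. People would give that consent on a description of the data that the procedure does not meet.

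**Working it through.** The point is a comparison of texts. Arithmetic is needed only to show how many people are affected.

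**Order of events, from sections 4.3.c, 5.1.c and 5.4.a**

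1. The respondent consents electronically to screening and answers the questions.
2. The respondent enters a college email when the questions are finished. The text says respondents, not eligible respondents.
3. The system determines eligibility, checks the address against earlier ones, and sends eligibility information only to valid, unused addresses.
4. The address sits in its own table, joined to the answers by an ID.
5. Ineligible people see an on-screen message and receive a resource list. Eligible people go on to trial consent.

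**Each statement in section 5.4.a against that order**

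- *Collected anonymously until eligibility is determined and consent is signed.* Steps 2 and 4 contradict this outright. An identifier is taken at step 2, ahead of both events. Nothing done later can make the collection anonymous.
- *Retained without identifiers if ineligible.* This can be true only if the join is cut after step 3. No section says that it is, or when. The end-of-study rule in section 5.4.b is written for study IDs. Whether it covers the screener's ID is not stated, and it would act only at the end in any case.

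**Does the design need the join for ineligible people?** The duplicate check compares one address with earlier addresses, so it needs a list of used addresses but not the answers behind them. The emailed invitation to the baseline survey needs the address of eligible people only. Neither function requires an ineligible person's answers to stay joined to an address.

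**Size, from the planning figures in section 4.4.b**

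- Enrolment per semester: 250 / 3 = 83.3, which reproduces the plan's figure of about 83.
- Screened per semester at 60% eligible: 83 / 0.60 = 138.3, which reproduces the plan's 138.
- Screened over three semesters: 138 × 3 = 414.
- Ineligible at 40%: 0.40 × 414 = 165.6, or roughly 165.
- Cross-check by subtraction: 414 − 250 = 164. This agrees because the plan's arithmetic assumes that every eligible person enrols.

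Phase I uses the same screener procedure and would add to this number. It is not counted here.

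**The case against.** The strongest reply is that the retention sentence in section 5.4.a is itself the rule. On that reading the join is made for screening, then stripped for ineligible people, and only the operational step is unwritten. This reading is possible for retention, and it limits what can be claimed. It does not rescue the statement that collection is anonymous, and a step on which the promise depends needs to be written down.

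The protocol also has real safeguards: separate tables, encryption, access limited to research staff, electronic consent to screening, and a planned Certificate of Confidentiality (sections 5.1.c, 5.4.a and 5.4.b). These stand as reductions of risk. They do not make joined data anonymous.

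A reader might infer more than the documents support:

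- **That ineligible people remain identifiable for good.** The documents do not say that the join is permanent, and the rule in section 5.4.b may remove it when the study ends.
- **That respondents are in fact told something untrue.** The wording of the screening statement is not in the documents reviewed. What can be said is that a statement following section 5.4.a would be inaccurate while the join exists.
- **That phone follow-up contradicts the plan.** Section 4.4.b says "Eligible participants who do not complete enrollment or who enroll but do not complete the baseline survey will be contacted by phone", while section 5.1.c takes phone numbers only after the trial consent signature. The call can be read as applying to people who signed and gave contact details but did not finish, so no change to it is needed on this ground.
- **That a number of under-age respondents can be given.** The age split in section 4.4.a describes enrolled students aged 18 to 29, not people who fail the screener.

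**Conclusion.** The contradiction holds and should be resolved before screening opens. The statement that collection is anonymous conflicts with the written procedure. The statement that retained data carry no identifiers is unsupported for as long as the join exists, because no section removes it at ineligibility.

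The size is roughly 165 ineligible Phase II respondents. This rests on the plan's 60% eligibility rate, its figure of 138 screened per semester, and the assumption that no unwritten step cuts the join. The count moves with the eligibility rate; the contradiction does not.

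This is a matter of consent and confidentiality. It has no bearing on randomisation, outcomes, sample size, power or analysis.

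**What to change.** 1. Program the screener to delete the join between email and ID automatically when a respondent is found ineligible, or is eligible but does not consent within a stated time.
2. For the duplicate check, keep only a list of used addresses, or a hash of each, with no ID that leads back to answers.
3. Amend section 5.4.a and the screening statement to say that answers are coded and tied to a college email until that deletion, and carry no identifier afterwards. Describe the deletion step in sections 4.3.c and 5.1.c so that the sections agree.

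The cost is a small change to the web screener and revised consent wording. The one function lost is that staff can no longer look up what an ineligible person answered earlier. The duplicate check and the emailed invitation to eligible people work as before.

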#### 6. DATA AND SAFTEY MONITORING PLAN

6.1. Participant Safety: Monitoring Plan for Adverse Events: Participation of subjects in the Phase I trial will consist of using the prototype CARES app for alcohol risk reduction for 30 days, then participating in a qualitative interview with [name] (Co-I). Participants will also complete surveys at program enrollment and at day 30. For Phase II, participants will provide survey data at baseline and complete follow-up assessments at months 3 and 6. For both Phase I and II we will be clear during the enrollment process and in other communications with participants that we will not monitor the CARES text message feature in real time (i.e., that there is not an individual sending and responding to texts), as we do not want participants to assume that any potential expressions of distress will be seen immediately. The CARES system is designed as an alcohol educational tool and risk reduction tool, not as a medical monitoring device. However, during the intervention period we will review our study participant's CARES text messages daily for descriptions of dangerous alcohol-related events or emotional distress. We will contact participants whose welfare we are concerned about and [name] will determine whether a referral or additional action is necessary.

In addition, at the start of the study (both Phase I and Phase II), all participants will be given the study phone number to program into their cell phones. Participants will be instructed to call the phone number if they are experiencing problems related to the study or to alcohol-related issues. Staff will route these calls to [name]. Contact numbers and email will remain available to all participants in the study through month 6. Finally, baseline and follow-up web-based survey responses will be viewed following each assessment.

**6.1.a.** Adverse Events: Throughout the intervention and follow-up phases, [name] (MPI) will report serious adverse events to The Miriam Hospital IRB immediately by telephone and by written report within 48 hours of our receipt of information regarding the event. The report will include information on the date of the event, what occurred, actions taken by the project staff, planned follow-up (if any), the intervention condition of the affected participant, whether the event appears to be related to the intervention, and whether the event affects future participation (i.e., will the participant continue in the study). [name] will provide a DSM report to the IRB and to the NIH Project Officer on an annual basis as part of the progress report. The DSM report will include a summary of all adverse events and serious adverse events, and all actions or changes that occurred as a result of these events.

